Office Title:

Repetitive Transcranial Magnetic Stimulation (rTMS) for Nicotine Addiction

NCT#:

NCT02401672

Document Date:

8/21/2014

Study Title: Developing rTMS as a potential treatment for nicotine addiction

PI: [name]

SPECIFIC AIMS

Cigarette smoking is the leading cause of preventable death in the United States^{1, 2}. Unfortunately smoking cessation is difficult, with the majority quit attempts resulting in relapse³⁻⁵ and the average smoker attempts to quit five times before a successful quit attempt. While a number of pharmacotherapeutic agents and cognitive behavioral therapies alone or in combination with medication have demonstrated efficacy ^{5, 6}, even with combined treatment, the most common outcome at one-year following a quit attempt is relapse ⁷. Only 6% of the 35 million smokers who report wanting to quit each year are successful in doing so for more than a month ^{8, 9}. Clearly, there is room for improvement in smoking cessation treatment.

Human brain imaging studies have provided insight into the brain regions associated with cue-induced cigarette craving, a frequent cause of relapse¹⁰⁻¹². Furthermore, improved ability to resist cue-induced craving is associated with a reduction in cue-induced activation of limbic and prefrontal brain regions ¹²⁻¹⁴. Transcranial magnetic stimulation (TMS) provides a non-invasive means of modulating brain neural activity^{15, 16}. Neuroimaging studies of repetitive TMS (rTMS) over dorsal lateral prefrontal cortex (DLPFC) demonstrated that rTMS normalized brain areas of anomalous activity due to depression^{17, 18}. Given this previous research, rTMS may reduce cue craving to smoking and treat nicotine dependence through modulating cortical and subcortical areas associated with smoking cue-induced craving.

To date, several studies have reported that rTMS reduced cue craving in nicotine dependence ¹⁹⁻²². However, these studies are limited by small sample sizes, variation in stimulation parameters, and in some cases the lack of sham-controlled design and objective measures of tobacco smoking. Furthermore, in all of these studies, stimulation location was targeted to a fixed brain region based on standard skull landmarks. rTMS studies in depression have showed that antidepressant effects are likely depend on coil positioning ^{23, 24}. Personalized coil placement based on a pre-treatment MRI has the potential to enhance outcomes. Additionally the duration or reduced craving following rTMS has yet to be examined. Taken together, while rTMS has demonstrated promise in facilitating smoking cessation, further double-blind investigation is required to determine optimal stimulation parameters and the duration of effect of rTMS in smokers. Furthermore, MRI guided TMS may help us to identify the optimal stimulation location to enhance the effectiveness of the treatment.

This R21 will build on exciting pilot work and advance our knowledge concerning the potential utility of rTMS in smoking cessation by conducting a controlled, double-blind method comparing the impact of ten daily treatments of active rTMS and sham rTMS, on cue-induced craving and cigarette consumption in nicotine-dependent cigarette smokers with extensive monitoring of side effects and smoking outcomes. We propose to directly stimulate the left DLPFC with Brainsight in smokers. In the two years of project, we plan to recruit 42 cigarette males and females of all ethnic and racial groups between the ages of 18 and 60 to participate in the study. Specific Primary Aims include:

Aim 1: To determine under rigorous experimental conditions, whether 10 MRI guided rTMS of left DLPFC treatment sessions over a 2 week period result in superior clinical outcomes compared to sham rTMS in smoking cessation.

Hypothesis 1: We hypothesize that 10 rTMS sessions (15 minutes 10 Hertz active rTMS at 100% resting motor threshold-rMT) over DLPFC will significantly reduce cue-elicited craving and cigarettes per day as compared to sham rTMS.

Aim 2: To evaluate the longevity of clinical benefit of 10 rTMS sessions on smoking measures including cigarettes per day and level of nicotine dependence with following-up 3 months after the last rTMS session.

Hypothesis 2: We will predict that the effects of rTMS will dissipate over 3 months following-up time in some smokers. We also will predict that the effects of rTMS will last more than 3 months in other smokers. The following-up data will provide the best fit of the relapse-time data relative to a variety of parametric alternatives.

Aim 3: To demonstrate whether the active rTMS and sham groups differ significantly in side effect profiles, and whether the frequency and severity of side effects decreases over the course of treatment.

Hypothesis 3: The frequency and severity of side effects will not differ between the active rTMS and sham groups, and decreases over the course of the treatment, suggesting adaptation or tolerance.

RESEARCH STRATEGY

1. Significance

Nicotine dependence remains a significant public health concern. In 2011, the World Health Organization (WHO) reported that tobacco use continues to be the leading global cause of preventable death, killing nearly 6 million people and causing hundreds of billions of dollars of economic damage worldwide each year ²⁵. In the United States, cigarette smoking is the leading preventable cause of mortality accounting for approximately 1 out of every 5 deaths ¹. On average, smokers die 13 to 14 years earlier than nonsmokers ²⁶. Cigarette smoking is the most common form of tobacco use and 45.3 million persons (19.3% of the population) are current cigarette smokers. Additionally the estimates for average annual smoking-attributable productivity losses are \$96.8 billion and the total economic burden of smoking is approximately \$193 billion per year ²⁷.

The 2010 National Health Interview Survey revealed that approximately 70% of current smokers want to quit and 41% have tried to quit, however few of these attempts were successful with only 4.7% of current smokers able to stop smoking for at least three months ². Despite the availability of therapeutic options for smoking cessation, only 6% of the 35 million smokers who report wanting to quit each year are successful in doing so for more than a month ^{8, 9}. **Clearly, there is room for improvement in smoking cessation.**

One particularly salient feature of nicotine-dependent cigarette smoking is the ability of associated environmental cues to elicit craving and cigarette-seeking behaviors. The systematic study of craving has occurred primarily via cue reactivity paradigms ^{28, 29} in which nicotine-dependent individuals are exposed to cues previously associated with smoking (e.g., cigarette, lighter, ashtray) and subjective craving and physiological reactions are measured ^{30, 31}. Numerous laboratory-based studies, including studies conducted in our laboratories at Medical University of South Carolina (MUSC), have demonstrated that exposure to smoking-related cues elicits robust craving and measurable physiological reactivity among smokers ³². These findings represent some of the most compelling evidence in support of a causal relationship between craving and cigarette smoking. Thus, the concept of craving has become an important focus of studies on smoking behavior, relapse and smoking cessation treatment. In conclusion, these findings imply that escalation of withdrawal symptoms, craving, and smoking urges during a quit attempt may contribute to smoking relapse. The reduction of cue craving and smoking urges may facilitate the treatment of nicotine dependence and prevent relapse during a smoking quit attempt.

Transcranial magnetic stimulation (TMS) is a noninvasive (and relatively painless) brain stimulation technology that can focally stimulate the brain of an awake individual ^{33, 34}. A localized pulsed magnetic field transmitted through a TMS coil is able to focally stimulate the cortex by depolarizing superficial neurons ^{35, 36} inducing electrical currents in the brain ¹⁶. If TMS pulses are delivered repetitively and rhythmically, the process is called repetitive TMS (rTMS). rTMS for the treatment of depression was approved for one manufacturer by the U.S. Food and Drug Administration (FDA) in October, 2008 ^{37, 38} and for a different device in January 2013. Researchers are investigating rTMS potential treatment effects in other neuropsychiatric disorders (schizophrenia, pain, alcohol, cocaine, stroke) ³⁹. **Taken together, TMS techniques could be used to improve the efficacy of smoking cessation.**

To date, several human studies have begun to evaluate the effects of rTMS applied to the lateral or medial prefrontal cortex on cue-induced craving and cigarette consumption 19-22. In one study, investigators²⁰ administered high frequency rTMS to the left DLPFC of treatment-seeking smokers. Subjects received 20 trains of either real or sham rTMS (20Hz, 90% motor threshold, 2.5 secs-on, 42.5 sec intertrain intervals for a total of 1000 pulses) over the left prefrontal cortex. While real rTMS was associated with significant reduction in terms of the number of cigarettes smoked in comparison with sham stimulation (p < .01), levels of craving did not differ significantly between the groups. In contrast, Amiaz and colleagues reported that rTMS (100% rMT, 10Hz, 20 train/day, total 1000 pulses) of the DLPFC reduced both cigarette craving and consumption ¹⁹. In a preliminary parallel-groups sham-controlled trial of rTMS in combination with the nicotine patch in heavily nicotine-dependent smokers with schizophrenia 40, rTMS did not increase abstinence rates, but did significantly reduce tobacco cravings induced by short-term (30-60 minutes) abstinence, which was assessed before application of the nicotine patch. More recently, Rose and colleague used 10 versus 1-Hz TMS over the superior frontal gyrus (SFG) in 15 volunteer smokers and found that craving after smoking cue presentation was elevated in the 10-Hz SFG condition, whereas craving after neutral cue presentations was reduced ²². These preliminary studies suggest that the location of the stimulation is critical and high frequency rTMS of the DLPFC, but not the medial area, might attenuate nicotine consumption and craving. Taken together, the significance of these effects are limited and further investigation is required to identify the appropriate stimulation parameters and targets needed to enhance the effectiveness of the treatment. As such, future replication studies using a valid sham TMS and exploring the number of treatments and duration of effects are greatly needed to further investigate the therapeutic potential of rTMS in nicotine dependence. In particular, future studies using MRI to guide location will help to optimize the parameters for the use of rTMS in the treatment of nicotine addiction.

In conclusion, nicotine dependence is the leading preventable cause of mortality in the world today. In spite of treatment advances, there is much room for improvement in the therapeutic approaches. Recent advances make it possible to utilize rTMS to modify behavior, cognitions and regional brain activity. Preliminary trials suggest potential therapeutic applications of rTMS in the area of nicotine dependence. The purpose of this proposal is to preliminarily explore the efficacy of 10 daily MRI-guided DLPFC rTMS in decreasing cue-induced craving and cigarette consumption in nicotine-dependent cigarette smokers. Information gathered through this study will inform future studies in terms of optimal parameters for the use of rTMS in the treatment of nicotine-dependent smokers.

2. Innovation

As mentioned above, several previous studies have demonstrated that rTMS applied to the lateral or medial prefrontal cortex can impact cue craving and/or consumption of cigarettes ¹⁹⁻²². However, in all studies to date the form of sham TMS did not cause similar scalp or facial sensation compared to real TMS leading to questions about the validity of the comparisons. In the proposed study, we will use an active E-sham condition ^{41, 42} which produces scalp/facial sensations that are comparable to rTMS. In addition, studies to date have used a 5 cm rule for prefrontal location determination which is imprecise and as many as 30% of participants may have been treated over the supplementary motor area rather than the prefrontal cortex ⁴³. Finally, a meta-analysis ⁴⁴ and a prospective clinical trial ⁴⁵ suggest that use of a greater number of rTMS stimulations may be more effective in depression treatment. Previous rTMS studies in smoking used 1000 pulses, much less than the dosage of TMS pulses demonstrated to be efficacious in depression, and higher doses have not been explored. This R21 proposal is innovative in three respects: this is the first time that a double blind rTMS study will be compared to an active E-sham stimulation in smokers; in addition, we will use MRI to determine stimulation site over prefrontal cortex; finally, we will employ more stimulation pulses (3000 pulses) than previous studies, allowing us to quantitatively and qualitatively investigate both short and longer term effects of rTMS in smoking cessation.

RESEARCH PLAN

[figure not shown]
Rationale. Several lines of evidence suggest that repetitive TMS (rTMS) over the left DLPFC can affect processes involved in nicotine addiction. First, stimulation of the DLPFC can induce release of dopamine in the

caudate nucleus ⁴⁶. Therefore, repeated stimulation may induce neuroadaptations in the dopaminergic system. Moreover, while administration of drugs induces an acute increase in dopamine levels, during withdrawal dopaminergic activity is reduced. Decreased dopaminergic activity has been associated with increased levels of craving and relapse ⁴⁷. Therefore, it is possible that even transient increases in dopamine released by TMS may help reduce levels of craving ⁴⁸. Second, the effects of brain stimulation can extend beyond the directly targeted area, including cross-hemispheric cortical and subcortical activity in remote neural networks connected to the stimulated regions ^{49,50}. Therefore, given the ability of TMS to modulate cortical excitability, it is possible that TMS can alter neuroadaptations and synaptic plasticity in the brain reward system. Third, it is well known that the PFC is strongly implicated in drug-seeking behaviors. The DLPFC plays an executive role in controlled response inhibition through its connectivity. Therefore, it is possible that repeated DLPFC stimulation could lead to improved inhibitory control and thereby reduced levels of drug-seeking. These theoretical underpinnings have led researchers, including our group at MUSC, to conduct pilot studies to explore the impact of rTMS of the left DLPFC in reducing craving for cigarettes ^{19, 20, 22}.

[figure not shown]
Several studies have shown that stimulation of the motor cortex can produce inhibitory or excitatory intermediate effects (lasting several minutes) following stimulation ^{51, 52}. Investigations of the intermediate effects of TMS have been used to develop a better understanding of brain functioning with respect to movement, vision, memory, attention, speech, neuroendocrine hormones and mood ⁵³⁻⁶⁰. Longer-term effects of TMS (days to weeks) are not well understood at a neurobiological level, but there is some evidence to support longer-term effects on mood, seizure activity and pain ⁶¹⁻⁶⁴. As discussed above, rTMS for the treatment of depression was approved by the FDA in 2008. Thus, we hypothesize that 10 sessions daily active rTMS will induce a longer lasting decrease in cue-induced craving and a reduction in cigarette consumption.

In a recent pilot project conducted by our research team, rTMS at 100% resting motor threshold (rMT), 10 Hz,

5 seconds on, 10 seconds off, total 3000 pulses over DLPFC was tested in 14 non-treatment seeking nicotine-dependent smokers ⁴². Compared to sham TMS, one session of high frequency DLPFC rTMS significantly reduced smoking cue-induced craving (Figure 1). In addition, the correlational analyses showed that the effect of rTMS on cue craving was positively correlated with Fagerstrom Test for Nicotine Dependence (FTND) score (Figure 2). This study was the first to show a clinically significant reduction in craving after prefrontal rTMS. However, we were not able to measure the

duration of effect or whether repeated sessions might have added therapeutic effect. The

current proposal extends this study, advancing it in a step-wise manner to a potential treatment. Further, we will use MRI to determine stimulation site instead of the imprecise 5 cm rule. Additionally, we will employ 10 session rTMS over two weeks period. We hypothesize that rTMS with the MRI TMS navigation will reduce cue-induced craving and cigarettes per day more than will sham TMS.

TMS research has been ongoing in the Brain Stimulation Laboratory (BSL) at MUSC for the past 15 years. The members of the BSL have been actively researching TMS in depression^{41, 50, 65-67}, schizophrenia ⁶⁸, post-

[figure not shown]
traumatic stress disorder (ongoing), Tourette's syndrome ⁶⁹, alcohol dependence (unpublished data), methamphetamine (paper in preparation), food craving ⁷⁰ and cigarette smokers ⁴². [name] is one of the world leaders in refining the use of TMS to treat depression and other neuropsychiatric and substance use disorders. Additionally, we have also studied other minimally invasive brain stimulation technologies such as transcranial direct-current stimulation (tDCS) ⁷¹, electroconvulsive therapy (ECT) (ongoing), deep brain stimulation (DBS) ⁷² and vagus nerve stimulation (VNS) ⁷³ for over a decade. In conclusion, the research group assembled for this project has vast experience in the use of TMS in clinical trials on neuropsychiatric diseases, including substance use disorders.

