- 4). Weekly Assessments: At the end of the 5th and the 10th treatment and 1 week and 1 month follow-up visits, subjects will complete FTND, MNWS-R, Tobacco diary, mCEQ and adverse events.
- 5). At the end of the experiment, subjects will be asked what treatment (active or sham) he/she believes was completed.
- **9. Follow-up (Specific Aim 2).** The treatment period of the study will conclude on the end of two weeks. Participants will then enter the follow-up phase of the study. The two follow-up visits will be scheduled one 1 week and 1 month after the 10th rTMS session. Data will include craving ratings, tobacco diary, CO, QSU-B and FTND. We will conduct a follow-up phone survey of participants 3 months after the 10th treatment. Cigarette consumption will be evaluated by asking: 'How many cigarettes do you now smoke on an average day?'. Craving will be assessed by asking: 'How much do you want to smoke a cigarette right now on a scale from 1 to 10?' and "When was your last cigarette?'. Nicotine dependence will be assessed by the FTND.
- 10. Data Analyses. All data will be analyzed in consultation with Data Coordination Unit (DCU) at MUSC. Quantitative measures of nicotine dependence: Craving rating panel, Tobacco diary, CO, QSU-B and FTND. Side effects: Following standard procedures, frequency and severity measures of side effects will be constructed from the clinical measures. Significance testing: All tests will be two-sided, performed at significance α =0.05, except where noted. The statistical approach will use an ANOVA for each outcome variable. Some data may be longitudinal as well as cross-sectional and we will include random effects to account for within-subject correlation.

Power Analysis. The primary efficacy of rTMS for this study will be the abstinence rate and the number of cigarettes smoked per day at the end of treatment. One previous study of rTMS reported that 10 sessions of rTMS significantly reduced the number of cigarettes per day by the 10^{th} treatment ($18.11 \pm 2.61 \text{ vs.} 10.71 \pm 2.19$) ¹⁹. A power analysis was conducted based upon this two group design, a power of 0.8, and an alpha level of 0.05; a significant difference is anticipated with 18 subjects in each group. The attrition rate in the above mentioned study was 8%. The attrition rate for our previous study was 12% ³¹. According to the attrition

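### Hypothesis 2 can hardly fail, reaches past the last contact and relies on an undefined relapse-time fit; restate it as an active-minus-sham difference up to 3 months

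*Combined protocol and SAP*

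**What the plan says.** Aim 2 (Specific Aims) concerns how long the benefit of ten sessions lasts "on smoking measures including cigarettes per day and level of nicotine dependence with following-up 3 months after the last rTMS session".

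The hypothesis attached to it has three parts:

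- The first part forecasts fading, without giving a proportion: "We will predict that the effects of rTMS will dissipate over 3 months following-up time in some smokers".
- The second part forecasts lasting benefit in the remainder, again without a proportion: "We also will predict that the effects of rTMS will last more than 3 months in other smokers".
- The third part turns to modelling and is the only analysis named: "The following-up data will provide the best fit of the relapse-time data relative to a variety of parametric alternatives".

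On follow-up, Section 9 says "The two follow-up visits will be scheduled one 1 week and 1 month after the 10th rTMS session", and later, on the final contact, "We will conduct a follow-up phone survey of participants 3 months after the 10th treatment". The call asks for average daily cigarettes, a craving score, the FTND and "When was your last cigarette". Table 1 marks FTND and the tobacco diary at all three follow-up contacts, including the call. The call as described in Section 9 does not mention the diary.

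Section 10 (Data Analyses) gives an ANOVA for each outcome, with random effects for longitudinal data, and two-sided tests at 0.05. It names no time-to-event method. The Power Analysis sizes the trial on end-of-treatment smoking and says the follow-up data will serve to power future studies.

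**The concern.** Three features of Hypothesis 2 cause trouble.

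1. **It has almost no way to fail.** Fading in some people and persistence in others is what most groups of smokers would show, treated or not. Hypotheses 1 and 3 both compare active with sham; Hypothesis 2 does not. In a single smoker, an effect of rTMS cannot be told apart from the natural course.
2. **It reaches past the data.** Nobody is contacted after 3 months.
3. **The only analysis it names is undefined.** No relapse event, quit date, time origin, censoring rule or list of candidate models appears anywhere, and Section 10 does not carry the analysis forward. The last-cigarette question dates the most recent cigarette, not the first one after stopping.

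At stake is one of three primary aims. A report that followed the hypothesis as written could declare it confirmed with no treatment effect. It would also not ask for what a future trial needs: a between-arm difference and its variability at each visit.

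**Working it through.** **The plan's own figures.** No sample size, event count or power is given for Aim 2. The only sizing is 18 evaluable per group for end-of-treatment smoking, inflated for 12% attrition: 18 / (1 − 0.12) = 20.5, rounded up to 21 per group, 42 in total. That step reproduces. The 18 is taken as given here.

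**Step 1: how often Hypothesis 2 would appear confirmed.** Let q be the proportion of an arm who look improved at 3 months for any reason. Take participants as independent, with n = 18. The hypothesis is contradicted only if none or all of them look improved, so

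P(mixed) = 1 − (1 − q)^18 − q^18.

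| q (assumed) | (1 − q)^18 | P(mixed) |
|---|---|---|
| 5% | 0.397 | 60% |
| 10% | 0.150 | 85% |
| 20% | 0.018 | 98% |
| 30% | 0.002 | over 99% |

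The q^18 term is negligible throughout. Nothing in the formula depends on the arm, so the sham group would confirm the hypothesis as readily as the active group at the same q.

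**Step 2: what the follow-up can show.** Contacts are at 1 week, 1 month and 3 months after the tenth session. A participant still benefiting at the call is right-censored there. Persistence to 3 months is observable; duration beyond it is not.

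**Step 3: whether a parametric relapse curve can be chosen.** The trial assumes no quit rate. As an assumed range, 42 × 0.20 = 8.4 and 42 × 0.30 = 12.6, so about 8 to 13 people would have stopped smoking. The favourable case gives each of them an exact diary date up to day 90. Data were simulated from a Weibull (shape 0.7, scale 45 days) or a lognormal (median 30 days, sigma 1.3), and AIC chose the family.

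- With 3, 8 or 13 quitters (400 runs per setting), the true Weibull was chosen in 8% to 21% of runs and the true lognormal in 21% to 46%.
- A repeat with 13 quitters, choosing among exponential, Weibull and lognormal, gave 24% and 40% (Monte Carlo standard error about 2 percentage points).

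The simulation settings are assumptions. Under them, the true family was missed in more than half of runs.

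**Step 4: what Aim 2 can deliver from the data already planned.** For a between-arm difference in means with 18 per arm, in SD units and unadjusted for baseline:

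- 95% CI half-width = t(0.975, 34) × √(2/18) = 2.032 × 0.333 = 0.68 SD.
- The difference detectable with 80% power is 0.96 SD with 18 per arm, or 0.89 SD with 21.

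**The case against.** The strongest reply is that Aim 2 is sound and only the wording of its hypothesis is loose. Cigarettes per day and FTND are collected from both randomised arms up to 3 months, and Section 10 already allows random effects for repeated measures. This stands. A reader might infer that Aim 2 cannot be answered, but the documents do not support that.

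Other points on that side:

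- **The hypothesis is not strictly irrefutable.** A unanimous outcome would contradict it, and at q = 5% that happens in about 40% of trials. This stands; the accurate description is nearly irrefutable.
- **The number of quitters is not documented.** A reader might apply the background rates of 4.7% and 6% in the Significance section to the 42 participants. Those rates describe people who stayed off cigarettes for at least three months or for more than a month. They leave out people who stop briefly and relapse, and they describe smokers at large, whereas these participants are seeking treatment. They cannot be used to count relapse times.
- **Relapse need not require quitting.** It could mean a return towards baseline consumption, and then everyone could contribute and the small-count argument would weaken. That is possible, but the plan does not say so, which shows that the event is undefined.
- **Relapse dates after 1 month need not be lost.** Table 1 marks the diary at 3 months, so a reader should not conclude that timing stops at day 30. Step 3 grants the diary dates, and model choice is still poor.
- **The trial is exploratory.** Its main efficacy measures are at the end of treatment, and follow-up is meant to inform later studies. This lowers the stakes but favours an estimate over a prediction that nearly any result satisfies.

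**Conclusion.** The point holds in a limited form. Hypothesis 2 and its relapse-time fit are wrong as written; Aim 2 and its data collection are not.

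- With 18 per arm, a mixed result would appear to confirm the hypothesis about 60% of the time if 5% look improved, and at least 98% of the time for q from 20% to 50%, with or without a treatment effect. This assumes independent participants and a common q.
- The reach beyond 3 months is a lesser fault, since persistence up to that point is observable.
- The curve fit is undefined whatever the number of quitters. That it is also unreliable rests on the assumed 20-30% quit rate and the simulated relapse distributions.

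A between-arm estimate at 3 months is feasible, but with a half-width near 0.68 SD it is an input to planning, not a powered test.

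**What to change.** 1. Restate Hypothesis 2 as the active-minus-sham difference in cigarettes per day, and in FTND, at 1 week, 1 month and 3 months after the tenth session.
2. In Section 10, specify one mixed model per outcome with arm, visit, arm-by-visit and the baseline value, using the random effects already allowed. Report the difference at each visit with its 95% CI, and say that it is an estimate for planning future studies.
3. Limit the claim to persistence up to 3 months.
4. Delete the "best fit of the relapse-time data relative to a variety of parametric alternatives" analysis, or reduce it to a descriptive listing among those abstinent at session 10, with abstinence and relapse defined.
5. State whether the diary or the call question supplies cigarettes per day at 3 months, so that Table 1 and Section 9 agree.

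The cost is protocol and analysis-plan wording; no new data are needed. The claim of effects beyond 3 months is given up.

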rate from our study (which is more conservative), we will randomize 21 subjects per group (total N=42) to have ample power to detect a clinically meaningful difference. We will use 1 week, 1 month and 3 months follow-up data to calculate power for future R01 studies.

HUMAN SUBJECTS RESEARCH Protection of Human Subjects

- 1. Human Subjects Involvement and Characteristics. Subjects will be women and men aged 18 to 60 years. Subjects meeting inclusion/exclusion criteria (see detail in Study Plan) will be offered participation, regardless of racial/ethnic group. The sample composition will reflect the Charleston-area population distribution of healthy adult smokers.
- 2. Sources of Materials. Research material obtained from the individual subjects will include psychiatric examination results, drug (including nicotine) use assessment results, urine for cotinine levels, expired air breathalyzer alcohol and CO tests, blood samples, heart rate, skin conductance, and subjective ratings (e.g., craving). Urine samples for the urine drug screen and pregnancy will also be obtained. Research data will be obtained specifically for research purposes. We will not use existing specimens, records or data.
- 3. Potential Risks. Investigational Device Exemption: Transcranial Magnetic Stimulation is an investigational device. The IRB at MUSC (in cooperation with the FDA) has determined repetitive TMS to be a non-significant risk intervention.
 - 1). *Potential Risks of TMS:* The major risk using repetitive TMS subjects is the possibility of inducing a seizure. We have now studied and given rTMS to more than several hundred subjects over past 15 years. None of these patients has developed a seizure. We will exclude patients with a prior history of seizures. We have reported that single session doses of 12,960 stimulations were safely given to volunteers with inducing seizures ⁸⁵. We will carefully adjust each person's stimulus intensity to his or her motor threshold, before beginning treatment.
 - 2). Potential hearing loss: The discharge of the rTMS coil generates a high-energy click that may cause cochlear damage. Foam earplugs can protect against these changes and will be worn by the subjects and the researchers present during TMS sessions.
 - 3) Potential risks of active Sham TMS: When subjects receive sham TMS they may experience mild discomfort on their scalp.

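### Aim 3 predicts that side effects will not differ between active and sham rTMS, but plans only a difference test, with no margin or confidence interval, at 18 to 21 per arm

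*Combined protocol and SAP*

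**What the plan says.** Aim 3 is one of the three aims listed as primary in the Specific Aims. It sets out "To demonstrate whether the active rTMS and sham groups differ significantly in side effect profiles", and whether side effects lessen during treatment. Hypothesis 3 then predicts: "The frequency and severity of side effects will not differ between the active rTMS and sham groups". It also predicts a decline over the course of treatment.

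Section 10 (Data Analyses) says that "frequency and severity measures of side effects will be constructed from the clinical measures". It names no scale, SD, expected rate or relevant difference. The testing rule is general: "All tests will be two-sided, performed at significance" level 0.05 unless noted otherwise, and "The statistical approach will use an ANOVA for each outcome variable". Where data are longitudinal, "we will include random effects to account for within-subject correlation". No exception is noted for side effects.

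Side effects are rated on a visual analog scale before and after every session (TMS Procedures, item 9), and there are ten sessions. The Power Analysis names abstinence and cigarettes per day as the efficacy outcomes and gives figures only for cigarettes per day. It arrives at 18 per group, raised to 21 for attrition.

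**The concern.** The aim asks whether there is a significant difference, the hypothesis predicts that there is none, and the only planned tool is a test of difference. Under that plan the one result that could be put forward for Hypothesis 3 is a non-significant p-value. Such a value can mean that the arms are similar, or that the study was too small or the ratings too noisy to tell. Less information makes the favourable result more likely.

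What is at stake is the tolerability conclusion of a primary aim in a study meant to inform a larger trial. A real excess of side effects on active rTMS could be written up as no difference. The second half of Hypothesis 3, the decline over treatment, is not affected, because it predicts a change that a significance test can support.

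**Working it through.** **Inputs from the documents.** Randomization 1:1; 21 per arm randomized and 18 per arm after attrition; two-sided alpha 0.05; ANOVA per outcome (with two groups, the same as a two-sample t-test); ten sessions with side-effect ratings.

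**Assumptions, because the documents give no figures.** An excess of 0.5 SD on active rTMS; within-person correlation between sessions (ICC) of 0.3 to 0.7; incidence of a given side effect of 10% vs 30% or 20% vs 40% (sham vs active).

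**1. The plan's own figure.** With 12% attrition, 18 / 0.88 = 20.5, which rounds up to 21, so the step from 18 to 21 reproduces. The 18 does not follow from the printed cigarette figures if the ± values are SDs: 7.40 / 2.41 = 3.07 SD, which needs about 3 per group. That is a separate matter. Only the planned group sizes are used below.

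**2. One severity score per person.** Power comes from the noncentral t distribution with noncentrality d × √(n/2) and 2n − 2 degrees of freedom. For d = 0.5 the noncentrality is 1.62 at n = 21 and 1.50 at n = 18.

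| | 21 per arm | 18 per arm |
|---|---|---|
| Miss rate, 0.5 SD | 64.7% | 69.2% |
| Miss rate, 0.8 SD | 28.4% | 35.5% |
| Difference detectable with 80% power | 0.89 SD | 0.96 SD |

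**3. Ten sessions averaged, 0.5 SD taken per session.** The mean of ten ratings has variance (1 + 9 × ICC)/10 in units of the single-session variance, so the effective difference is 0.5 / √((1 + 9 × ICC)/10).

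| ICC | Effective difference | Missed, 21 per arm | Missed, 18 per arm |
|---|---|---|---|
| 0.3 | 0.82 SD | 26% | 33% |
| 0.5 | 0.67 SD | 43% | 50% |
| 0.7 | 0.59 SD | 54% | 60% |

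**4. Share of participants with a given side effect.** Exact enumeration; the lower figure is ANOVA on 0/1 data, the higher is Fisher's exact test.

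| Sham vs active | Missed, 21 per arm | Missed, 18 per arm |
|---|---|---|
| 10% vs 30% | 63-74% | 68-80% |
| 20% vs 40% | 72-81% | 74-84% |

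**5. What an interval would show, one score per person.** The 95% half-width is t(0.975, 2n − 2) × √(2/n):
- 21 per arm: 2.021 × √(2/21) = 0.62 SD.
- 18 per arm: 2.032 × √(2/18) = 0.68 SD.

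Both exceed 0.5, so an observed difference of exactly zero leaves a 0.5-SD excess inside the interval. If the arms are truly equal, p > 0.05 occurs 95% of the time, but the upper 95% limit falls below 0.5 SD only 35% (n = 21) or 31% (n = 18) of the time.

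**The case against.** **The decision rule is inferred.** No sentence says that non-significance confirms Hypothesis 3. Aim 3 is neutral, and the hypothesis can be read as an expectation. This stands as a limit on the claim: a reader might infer that the protocol declares equal tolerability whenever p > 0.05, and the documents do not say so. They do leave no other planned route to supporting the hypothesis.

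**The miss rate depends on the reviewer's choices.** This also stands. The 0.5 SD is an illustration, and the 65-69% applies to one score per person. A reader might infer that a relevant excess would usually be missed. That fails when ten sessions are averaged at a correlation of 0.3 to 0.5, where 26-50% are missed, and for a 0.8-SD excess on one score. Hypothesis 3 also covers both frequency and severity. If each carried a 0.5-SD excess and the two were independent, both would be missed only about 42-48% of the time (0.647² and 0.692²).

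**The power statement concerns efficacy.** The plan says "we will randomize 21 subjects per group (total N=42) to have ample power to detect a clinically meaningful difference", and a reader might take that to cover side effects. It closes a paragraph about smoking outcomes, so it makes no claim about Aim 3 and needs no change on this account.

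**The sham is itself an active comparator.** It delivers scalp current by design and may cause mild discomfort (Potential Risks). An upper limit on active minus sham therefore bounds the excess over this sham, not tolerability in itself. The fix should say so.

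**This is a small exploratory study with ordinary safety reporting.** Adverse events are recorded around each session by masked staff and reported to the IRB, and nothing here weakens that. But an exploratory study can state its precision, and a formal margin is not being asked for.

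**Conclusion.** The concern holds in this limited form: a no-difference hypothesis under a primary aim is paired with a difference test only, and no margin, interval or side-effect power is planned. That mismatch depends on no assumption. At 18 to 21 per arm, non-significance cannot support the hypothesis. For one score per person, the data could exclude only excesses larger than about 0.62 to 0.68 SD even if the observed difference were zero, and power reaches 80% only at about 0.89 to 0.96 SD.

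The chance of missing a real excess is less certain. It runs from 26% to 69% for an assumed 0.5 SD, depending on whether sessions are averaged and how strongly they correlate, and from 63% to 80% for an assumed 10% vs 30% incidence. The efficacy outcomes are unaffected. The change should be made, because it alters what Aim 3 can conclude.

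**What to change.** Reword Aim 3 and Hypothesis 3 as estimation, for example: *We will estimate the active-minus-sham difference in the frequency of side effects (risk difference) and in their severity (mean difference, using the planned random-effects model for per-session ratings), each with a two-sided 95% confidence interval.* The prediction of a decline over treatment can stay.

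Add to section 10 that:
- conclusions about excess side effects relative to the active sham will be read from the upper confidence limit;
- p > 0.05 will not be reported as no difference;
- the expected precision for one score per person is about ±0.62 to ±0.68 SD, with 80% power only for differences of about 0.89 to 0.96 SD.

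The cost is wording and intervals computed from data already planned, with no extra participants, visits or procedures. The downside is that the trial gives up the claim that side effects do not differ between the arms.
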